3. Vital signs: Blood pressure/pulse (supine): at baseline and on Day 1 of each treatment cycle, before treatment administration. Height (in cm or inches): at baseline only. Weight (in kilograms or pounds): at baseline and on Day 1 of each treatment cycle. ECOG performance status: at baseline and on Day 1 of each treatment cycle. Temperature (in °C or in °F): at baseline and on Day 1 of each treatment cycle. For patients remaining on treatment for a period of time more than 6 cycles and come back to the site every 3 cycles, vital signs (including blood pressure/pulse, weight, ECOG performance status and temperature) will be done in concomitance with the visit to the site (once every 3 cycles, 1.5 months). Following approval of Amendment 4, management of patients should be as per Section 9.5 4. ECG: 12-lead study. To be done at baseline, at the end of the last cycle and to be repeated during treatment as medically indicated 5. Chest X-Ray: Mandatory at screening visit and at the end of last cycle as safety assessment. 6. Ophthalmologic Examination: to be conducted at baseline, at the end of even cycles (between days 11 and 14) and at the end of last cycle. For patients remaining on treatment for a period of time more than 6 cycles and come back to the site every 3 cycles, opthalmological examination will be done in concomitance with the visit to the site (once every 3 cycles, 1.5 months). Includes visual acuity test and fundoscopic examination by an ophthalmologist. Additional assessments will be performed if clinically indicated. Ophthalmologic evaluations will be possibly done by the same ophthalmologist for a given patient. Following approval of Amendment 4, management of patients should be as per Section 9.5 7. Pregnancy Test: For women of reproductive potential. Must be done within 7 days prior to initial study treatment. 8. Urinalysis: pH, dipstick for glucose, protein and blood. To be done at baseline and at the end of last cycle. During treatment, should be performed at the end of even cycles (between days 11 and 14). For patients remaining on treatment for a period of time more than 6 cycles and come back to the site every 3 cycles, the urinalysis tests may be done locally when the visit to the site is not planned (one visit planned to the site every three cycles, 1.5 months) and must be sent to the site for safety evaluation and reported on CRF. Following approval of Amendment 4, management of patients should be as per Section 9.5 9. Hematology (local laboratory): Hemoglobin, erythrocytes (RBC), white blood cell (WBC) with differential count (neutrophils, lymphocytes, monocytes, eosinophils, basophils, differential other cells), platelets (PLTs). To be done at baseline and between Day 11-14 of each cycle. In case of toxicity preventing re-treatment, hematology should be re-assessed on Day 1 of the next cycle before starting treatment. For patients remaining on treatment for a period of time more than 6 cycles and come back to the site every 3 cycles, the hematological tests may be done locally when the visit to the site is not planned (one visit planned to the site every three cycles, 1.5 months) and must be sent to the site for safety evaluation and reported on CRF. Following approval of Amendment 4, management of patients should be as per Section 9.5 10. Blood Chemistry (local laboratory): sodium, potassium, chloride, magnesium, blood urea nitrogen (BUN) or urea, creatinine, albumin, AST/SGOT, ALT/SGPT, Alkaline Phosphatase (ALP), total bilirubin, creatinine clearance (calculated by Cockroft and Gault's formula), amylase and lipase. To be done at baseline and between Day 11-14 of each cycle. In case of toxicity preventing re-treatment, blood chemistry should be re-assessed on Day 1 of the next cycle before starting treatment. For patients remaining on treatment for a period of time more than 6 cycles and come back to the site every 3 cycles, the biochemical tests may be done locally when the visit to the site is not planned (one visit planned to the site every three cycles, 1.5 months) and must be sent to the site for safety evaluation and reported on CRF. Following approval of Amendment 4, management of patients should be as per Section 9.5 11. Coagulation: INR (International Normalized Ratio), activated partial thromboplastin time (APTT in seconds). To be done at baseline, at the end of last cycle and, during treatment, at the end of even cycles (between Days 11 and 14). For patients remaining on treatment for a period of time more than 6 cycles and come back to the site every 3 cycles, the coagulation tests may be done locally when the visit to the site is not planned (one visit planned to the site every three cycles, 1.5 months) and must be sent to the site for safety evaluation and reported on CRF. Following approval of Amendment 4, management of patients should be as per Section 9.5 12. Tumor imaging: chest/abdomen/pelvic CT scan/ MRI : At baseline, to be done within 21 days before Day 1; during the treatment period (irrespectively from cycles duration), the first one to be done 6 weeks (between days 42 and 48) after first drug administration, the second one to be done 3 months (between days 92 and 98) after first drug administration, following ones to be repeated every 6 weeks (between days 42 and 48) after the previous one, and at end of last cycle (if not done in the previous 4 weeks). During Follow Up, to be performed every 6 weeks, until PD or until a new antitumor therapy starts. Patients with responding tumors (complete or partial response) must have response confirmed by CT scan at least 4 weeks after the 1st documentation of response. The same method of assessment and the same technique should be used to characterize and follow the same lesion at baseline and during treatment. CT scan is the desirable method for lesion measurement. Other measurement techniques (eg MRI) are acceptable (but not for lung lesions) provided that the size of the measurable lesion is twice the slice thickness of the MRI. After data cut-off of 31 May 2017, the patients should perfom CT scan according to routine clinical practice and/or at investigator's discretion. 13. Survival: To be assessed during Follow Up every 6 weeks until PD or until a new antitumor therapy starts; every 6 months thereafter, up to 2 years from the end of treatment. Following approval of Amendment 4, management of patients should be as per Section 9.5

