16. Biomarker Status Assessment: retrieval of tumor paraffin embedded blocks (slides), obtained from consenting patients before study entry (if available) and characterization of baseline molecular features of p53, p21, p27, cyclin D1, p75, TRKA and other genes/proteins involved in the PHA-848125AC mechanism of action.

17. Pharmacokinetics: blood samples may be collected if, in the opinion of the Investigator and of the Sponsor, an evaluation of PK parameters is needed for safety reasons.

18. Histological confirmation: histological confirmation of diagnosis of thymic carcinoma for all patients will be obtained by an Independent Review Committee during the course of the study, based on paraffin embedded tumor tissue slides retrieved from patients.

19. Enrollment: The Investigator is requested to sign a Request For Enrollment form. His/her signature is the guarantee that all the eligibility criteria are met. Patient Number is assigned by the Sponsor. Treatment must be administered within 7 days from patient enrollment.

20. PHA-848125AC administration: The study drug will be administered at 150 mg (flat dose) once daily for 7 consecutive days of each treatment cycle (from day 1 to Day 7). After an overnight fasting with free access to water, patients will take the study drug with a large glass of plain water without ice. A light breakfast can be served 1.5-2 hours later. PHA-848125AC capsules have to be stored under refrigerated conditions (5 ± 3 °C; 36-46 °F) and out of reach of children

(*) Cycle 1, Day 1 assessments: hematology, blood chemistry, urinalysis and coagulation do not need to be repeated before treatment on Cycle 1, Day 1 if they were performed during screening within 1 week before first study drug administration. Cycle > 1, Day 1 assessments: hematology and blood chemistry do not need to be repeated before treatment on Cycles> 1, Day 1 if no toxicity preventing re-treatment resulted from laboratory assessments done within the previous 4 days.

(§) AE FU: end of adverse events reporting period (to be done 28 days after last study drug administration) and follow up of unresolved drug related/serious AEs.

After data cut-off of 31 May 2017, AE/SAE data and related follow up will be no longer collected into the CRF, but assessments information should continue to be collected into the patient's medical notes.

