9.4.4. Retreatment and Dose Delay

A new cycle of treatment may begin when the ANC is $\geq 1500/\text{mm}^3$, the platelet count is $\geq 100,000/\text{mm}^3$, and the non-hematologic toxicities are \leq grade 1, except for alopecia (for which a grade > 1 is allowed) and for ocular toxicity (for which a worsening retinopathy of 1 or more grades compared to baseline implies study treatment discontinuation) or are recovered to baseline values, if grade 2 is allowed at study entry. If these conditions have not been met, treatment should be delayed for 1 or 2 weeks to allow for recovery. If after a maximum of a 2-week delay all toxicities (except for alopecia and for toxicities for which grade 2 is allowed at study entry) are \leq grade 1, then proceed with treatment as outlined in the Dose Modification Table 4. An increased delay > 2 weeks is to be discussed between the Investigators and the Sponsor on a case by case basis.

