9.4.10.9. Concomitant Radiotherapy

Palliative radiotherapy to specific sites is permitted if considered medically necessary by the treating physician. However, the irradiated area should be as small as possible, and involve $\leq 20\%$ of the bone marrow reserve [Appendix 2]. During the period of irradiation and for 2 weeks after, chemotherapy should be withheld. If irradiation-related toxicities (other than xerostomia) have not normalized to pre-irradiation levels after these 2 weeks of rest, the patient should be removed from the study. Radiotherapy should be avoided for at least 5 days after the last dose of PHA-848125AC.

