11.4.2. Laboratory Safety Assessments

Laboratory safety assessments will include repeated evaluation of hematology and biochemistry parameters, urinalyses and pregnancy test that after the cut-off date of 31 May 2017 will be done according to routine clinical practice and/or at investigator's discretion. The results of these exams should be recorded only in the patient's medical notes..

Hematology tests include: hemoglobin, erythrocytes (RBC), white blood cell (WBC) with differential count (neutrophils, lymphocytes, monocytes, eosinophils, basophils, differential other cells), platelets (PLTs).

They will be performed during screening period and repeated during treatment between the Days 11 and 14 of all cycles. If toxicity preventing re-treatment results from the Day 11-14 assessment, hematology should be repeated as needed to monitor for recovery.

Hematology tests will be done also on Day 1 of cycles, before study drug administration, only in case toxicity preventing re-treatment resulted from the assessment done within the previous 4 days at the end of the prior cycle.

For patients remaining on treatment for a period of time more than 6 cycles and come back

Tiziana Life Sciences, PLC - Confidential Page 71 of 101

Milciclib maleate (PHA-848125AC)	CDKO-125a-006-P4
Protocol for Study CDKO-125a-006	09 March 2017

to the site every 3 cycles, the hematological tests may be done locally when the visit to the site is not planned (one visit planned to the site every three cycles, 1.5 months) and must be sent to the site for safety evaluation and reported on CRF.

Blood chemistry tests include: sodium, potassium, chloride, magnesium, blood urea nitrogen (BUN) or urea, creatinine, albumin, AST/SGOT, ALT/SGPT, Alkaline Phosphatase (ALP), total bilirubin, creatinine clearance (calculated by the Cockroft and Gault's formula), amylase and lipase.

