They will be performed during screening period and repeated during treatment between the Days 11 and 14 of all cycles. If toxicity preventing re-treatment results from the Day 11-14 assessment, blood chemistry should be repeated as needed to monitor for recovery. Blood chemistry tests will be done also on Day 1 of cycles, before study drug administration, only in case toxicity preventing re-treatment resulted from the assessment done within the previous 4 days at the end of the prior cycle. For patients remaining on treatment for a period of time more than 6 cycles and come back to the site every 3 cycles, the biochemical tests may be done locally when the visit to the site is not planned (one visit planned to the site every three cycles, 1.5 months) and must be sent to the site for safety evaluation and reported on CRF.

Coagulation tests include: INR (International Normalized Ratio) and activated partial thromboplastin time (APTT, in seconds). To be done at baseline, at the end of last cycle and, during treatment, at the end of even cycles (between Days 11 and 14). For patients remaining on treatment for a period of time more than 6 cycles and come back to the site every 3 cycles, the coagulation tests may be done locally when the visit to the site is not planned (one visit planned to the site every three cycles, 1.5 months) and must be sent to the site for safety evaluation and reported on CRF.

Urinalysis includes: pH, dipstick for glucose, protein and blood. It will be performed at baseline and at the end of last cycle. During treatment, should be performed at the end of even cycles (between Days 11 and 14). For patients remaining on treatment for a period of time more than 6 cycles and come back to the site very 3 cycles, the urinalysis tests may be done locally when the visit to the site is not planned (one visit planned to the site every three cycles, 1.5 months) and must be sent to the site for safety evaluation and reported on CRF.

Serum/urine pregnancy test is indicated only for women of reproductive potential and is to be carried out within 7 days prior to the first treatment administration.

The timing and specific requirements for each laboratory safety evaluation are given in Section 7, Schedule of Events.

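### For a cycle started late after clean Day 11-14 labs, Section 11.4.2 and the Section 7 schedule disagree on whether Day 1 hematology and chemistry are needed

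*Protocol*

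**What the plan says.** **Section 11.4.2, hematology.** Tests are done at screening and between Days 11 and 14 of every cycle. Then: "Hematology tests will be done also on Day 1 of cycles, before study drug administration, only in case toxicity preventing re-treatment resulted from the assessment". The full condition is "only in case toxicity preventing re-treatment resulted from the assessment done within the previous 4 days at the end of the prior cycle". If the Day 11-14 result does prevent re-treatment, the test is also to be repeated as needed until recovery.

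**Section 11.4.2, chemistry.** The same rule: "Blood chemistry tests will be done also on Day 1 of cycles, before study drug administration, only in case toxicity preventing re-treatment resulted". The section closes by referring timing and requirements to Section 7.

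**Section 7, table and note (*).** Hematology and chemistry are marked X (*) on Day 1. For cycles after the first, note (*) drops the Day 1 repeat "if no toxicity preventing re-treatment resulted from laboratory assessments done within the previous 4 days".

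**Section 7, footnote 9** (footnote 10 is alike for chemistry): "In case of toxicity preventing re-treatment, hematology should be re-assessed on Day 1 of the next cycle before starting treatment". No age of the labs is mentioned. The synopsis carries copies of the table, the footnotes and the note.

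**Section 9.4.4.** A new cycle may begin once ANC is at least 1500/mm³, platelets are at least 100,000/mm³ and non-hematologic toxicity is grade 1 or less or back to baseline, with listed exceptions. Otherwise: "If these conditions have not been met, treatment should be delayed for 1 or 2 weeks to allow for recovery". No maximum age is given for the ANC and platelet values.

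**The concern.** The two main rules start from opposite defaults. In the Section 7 table the Day 1 test is due unless recent clean labs excuse it. In 11.4.2 it is not called for unless the end-of-cycle labs showed a problem. Both mention 4 days, but the words do different work: in note (*) they limit how old the excusing labs may be, while in 11.4.2 they describe the assessment whose bad result triggers the test.

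The difference matters when a cycle is held for something that is not a laboratory finding. Section 3.2.7 reports nausea, fatigue, diarrhea and tremors at 150 mg/day, and 9.4.4 holds the next cycle until non-hematologic toxicity has recovered. Palliative radiotherapy is another reason: "During the period of irradiation and for 2 weeks after, chemotherapy should be withheld". Such a patient may have clean Day 11-14 labs and a late Day 1. A site working from 11.4.2 could then apply the 9.4.4 count thresholds to values taken before the delay, and so omit a pre-dose safety check that note (*) requires.

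**Working it through.** **Inputs**
- Cycle length 14 days (9.4.1), so an on-time next Day 1 is Day 15 of the current cycle.
- End-of-cycle labs on Days 11-14 (11.4.2; footnotes 9 and 10).
- Waiver window of 4 days (note (*)).
- Delay of 1 or 2 weeks (9.4.4); a longer delay needs discussion with the sponsor.

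**Formula.** Age of labs at the actual Day 1 = (15 + delay in days) − lab day.

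**The plan's own figure.** With no delay: 15 − 14 = 1 day and 15 − 11 = 4 days. Labs are 1-4 days old, which reproduces the 4-day window.

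**Delayed cycles**
- 1 week: 22 − 14 = 8 and 22 − 11 = 11, so 8-11 days.
- 2 weeks: 29 − 14 = 15 and 29 − 11 = 18, so 15-18 days.

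**Are Day 1 labs called for?**

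| End-of-cycle labs at actual Day 1 | Table X and note (*) | 11.4.2 | Footnotes 9 and 10 |
|---|---|---|---|
| At most 4 days old, clean | No | No | No |
| At most 4 days old, preventing re-treatment | Yes | Yes | Yes |
| More than 4 days old, clean | **Yes** | **No** | Not triggered by the labs; no age condition |
| More than 4 days old, preventing re-treatment | Yes | Not by the Day 1 sentence, but covered by the repeat-until-recovery sentence | Yes |

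On-time cycles fall in the first two rows, where all the texts agree. In the fourth row 11.4.2 has its own provision for repeats. The conflict is the third row: clean labs followed by a late start.

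**The case against.** The best defence is that 11.4.2 simply describes the on-time cycle. Its condition presupposes an assessment made within the previous 4 days, so it carries a 4-day reference of its own. It says when tests will be done and does not forbid others. It also refers timing to Section 7, as does 11.1, and there the X on Day 1 makes testing the default. Section 9.4.4 adds that after a delay treatment resumes only if toxicities, with exceptions, are grade 1 or less, which is a condition at restart.

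Much of this stands, and it makes the matter a conflict of wording rather than an absent safeguard. It does not remove the conflict. Nothing in 11.4.2 says it is confined to on-time cycles. The cross-reference leads to a section where note (*) has an age condition and footnotes 9 and 10 have none. Section 9.4.4 gives no age for the counts it relies on.

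Some stronger readings are tempting but not supported:
- **Three separate rules.** A reader might take footnotes 9 and 10 to mean any toxicity, as against a laboratory one in 11.4.2. The wording allows that but does not establish it.
- **Labs weeks old in general.** Only the 2-week delay gives more than two weeks; a 1-week delay gives 8-11 days.
- **Restart after radiotherapy on stale counts.** The protocol gives no length of irradiation, so any age of labs is an assumption. Section 9.4.10.9 also removes a patient whose irradiation-related toxicities, other than xerostomia, have not returned to pre-irradiation levels after the 2 weeks of rest. That implies some reassessment, though no laboratory test is named.
- **Distorted laboratory tables.** Section 12.3.6 uses each patient's worst value over the whole treatment period, and every cycle has Day 11-14 labs. Nothing shows that extra pre-dose values after a longer rest would change these tables.

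**Conclusion.** The conflict is real but narrow. For a cycle started late after clean Day 11-14 labs, the Section 7 table with note (*) calls for Day 1 hematology and chemistry, and 11.4.2 taken literally does not. Under 11.4.2 the latest required values would be 8-11 days old after a 1-week delay and 15-18 days old after a 2-week delay, against at most 4 days under note (*).

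These figures assume labs taken within the Day 11-14 window, a delay of exactly 1 or 2 weeks for a non-laboratory reason, and no voluntary repeat by the site. Many investigators would repeat the tests anyway. The protocol does not say how often cycles are delayed, so the number affected cannot be given.

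The remaining reach is limited. Section 11.4.2 moves laboratory tests to routine practice or investigator discretion after 31 May 2017, and footnotes 9 and 10 defer to Section 9.5 once Amendment 4 is approved; this version is dated 09 March 2017. The point is still worth correcting, because following one stated rule omits a pre-dose check that another requires. Which rule is clinically right is not judged here.

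**What to change.** Reconcile the hematology and chemistry sentences of 11.4.2, footnotes 9 and 10 and note (*) of Section 7, and the synopsis copies into one rule. That rule should:
- say expressly what applies when a cycle starts late for any reason, including non-laboratory toxicity and radiotherapy; and
- be consistent with the 9.4.4 retreatment check, so that it is clear which values that check uses.

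The clinical team decides which rule applies, including any limit on the age of the values. Note (*) holds the only age condition now set on clean labs in cycles after the first.

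The cost is amendment wording in two paragraphs, two footnotes, one note and their synopsis copies. If the rule chosen requires the tests, it adds at most one routine local blood test per delayed cycle, which note (*) already calls for. The sample size, endpoints and planned analyses are unchanged.

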11.4.3. Other Safety Assessments

The following safety assessments will also be performed, according to timing reported in Section 7, Schedule of Events:

Physical examination will be done at pretreatment and on treatment at the end of each cycle. Any abnormality at pretreatment should be reported in the Baseline Signs and Symptoms CRF page and on treatment in the AE CRF page. For patients still on treatment at the cut-off date of 31 May 2017, assessments data should be recorded only in the patient's medical notes.

Vital Signs: Blood pressure/pulse (supine) is to be monitored at baseline and on Day 1 of each treatment cycle, before treatment administration; height (in cm or inches) will be measured at baseline only; weight (in kg or pounds) will be assessed at baseline and on Day 1 of each treatment cycle; ECOG performance status will be monitored at baseline and on Day 1 of each treatment cycle; temperature (in °C or °F) will be measured at baseline and on Day 1 of each treatment cycle.

ECG (12-lead) will be carried out at the pretreatment visit and at the end of last cycle. To be repeated during treatment as medically indicated.

Chest X-ray will be carried out, for safety assessment, at the pretreatment visit and at the end of last cycle.

Ophthalmologic examination will include visual acuity test and fundoscopic examination and will be carried out at the pretreatment visit, at the end of even cycles (between Days 11 and 14) and at the end of last cycle by an ophthalmologist. Additional assessments will be performed if clinically indicated.

Ophthalmologic evaluations will be done by the same ophthalmologist for a given patient. For patients still on treatment at the cut-off date of 31 May 2017, data should be recorded only in the patient's medical notes.

Neurological status evaluation: at each scheduled clinical visit (at baseline, at the end of each treatment cycle, and 28 days after the last dose of study drug administration) patients will undergo regular clinical examination, including the assessment of clinical tremors and associated signs and symptoms. Patients should be examined during rest, when assuming various positions and when moving (see also Section 9.4.7, Assessment and Management ofPotential CNS Toxicity). Any sign and symptom of neurological toxicity should be recorded in the Adverse Events CRF pages of the relevant cycle. For patients still on treatment at the cut-off date of 31 May 2017, no AEs will be collected in the CRF, and all evaluations should be recorded only in the patient's medical notes.

Tiziana Life Sciences, PLC - Confidential Page 73 of 101

